2.0 Objectives

2.0 Study Objectives

2.1 Research Design and Methods

Our goal is to better understand the biology of breast cancer stem cells and pleural effusion formation to improve therapy of malignant pleural effusion in breast cancer patients. Based on our preclinical studies described in the background section, a clinical trial is planned to answer specific questions regarding the role of histone deacetylation and effect of its inhibition on breast patients with MPE. In this study, eligible patients with recurrent symptomatic MPE who need an indwelling pleural catheter based on MDACC algorithms for placement will have one placed and will receive 10 weeks of VPA or placebo.

The first aim is to achieve a beneficial clinical effect of VPA on patients with MPE. The specific question is if VPA alters pleural effusion re-accumulation following placement of an indwelling pleural catheter to the extent that it will enable significant shortening of time to removal of the catheter compared to placebo. Additional aims will analyze the biology of histone deacetylation inhibition in MPE and will help to develop biomarkers of activity and noninvasive monitoring to such therapy:

The second aim is to analyze the amount of daily fluid drained with therapy. Patients will be provided a daily fluid drainage diary.

The third aim is to assess radiographic and clinical correlates using standard of care testing and assessment: Chest x-ray and CT to study effect on primary tumor burden and assessment of overall survival.

Our fourth aim is to study biological correlates. We will study the level of H3 and h4 hyperacetylation and inflammatory cytokines in the effusion and in the serum at baseline and at week 2. Fluid will be collected and stored if applicable from visits at baseline, at week 2, 6, and 10. We plan to study expression of stem cell markers on cells from effusion to demonstrate inhibitory effect of VPA on these cells. Urine will be collected and stored if applicable at baseline, weeks 2, 6, and 10 for correlative studies. Finally, we will study the effect of VPA therapy on level of circulating tumor cells.

Our fifth aim is to assess drug effect on patient symptoms, dyspnea and exercise tolerance using the EuroQOL, St George's respiratory questionnare and six-minute walk test respectively.

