6.0 Statistical Considerations

6.0 Statistical Considerations

Sample Size

The primary outcome for this study is time to pleural catheter removal because it is no longer needed to drain the pleura of fluid. Patients who have their catheter removed for other reasons will be censored as of the date of catheter removal. Patients who die before having their catheter removed will be censored on the date of death.

Preliminary data from 58 breast cancer patients with ECOG performance status 0, 1, 2, or 3 revealed a median time to catheter removal of 110 days with 95% confidence interval 56 to 328 days. Twenty-nine of these 58 patients had their catheters removed because they were no longer needed to drain the pleura of fluid.

Patients will be randomized to active treatment (valproic acid) or control. A sample size of 76 patients (38 on each arm) will yield 80% power to detect an improvement in median time to catheter removal from 56 days in the control arm to 28 days (hazard ratio = 2.0) in the active treatment arm with a 2-sided significance level of 0.05. We expect to enroll 3 patients per month. We will be able to detect a hazard ratio of 2.0 (control vs. experimental), regardless of the median for the control group. If the median for the control group is actually 110 days, then we will be able to detect a significant difference if the median in the experimental group is 55 days.

This sample size calculation includes an interim analysis for futility and for efficacy once 36 patients have had their catheters removed using the methods of Lan and DeMets. The interim analysis for efficacy will employ an O'Brien-Fleming stopping boundary with a nominal significance level of 0.0031, while the interim analysis for futility will employ a Pockock stopping boundary with a nominal significance level of 0.3217. The final analysis will use a nominal significance level of 0.049 and will be conducted after all patients have had their catheters removed. These sample size calculations were performed with East 5.0 (Copyright © 2007, Cytel Inc., Cambridge, MA). Sample size was calculated based on 50% reduction in median time to catheter removal secondary to improved fluid in the control.

Randomization

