We will estimate the rate of toxicity leading to dose reduction for patients on the active treatment with a 90% credible interval. If we have toxicity leading to dose reduction in 5 of the 40 patients on the active treatment, then our 90% credible interval for the rate of toxicity leading to dose reduction will be 6.6% to 23.6%. We will also report the posterior probability that the rate of toxicity leading to dose reduction for patients on the

active treatment is more than 25%.

We will tabulate adverse events by treatment arm, grade, and relationship to study drug.

Translational Studies

For CTC studies using the adnagen approach .3 ng/ml in GA733-2 or muc-1 will be considered positive and both conversion to negative and change from baseline (using continuous data) will be assessed. Descriptive statistics will be applied. Using the Veridex system 5 CTCs will be considered positive for all dichotomous analyses and conversion to negative and change from baseline will be assessed as above.

Statistically significant conversion to negative in the VPA arm in either test will be considered a significant change. CTC studies will be performed only if funds are available and will be done by [name] who has extensive experience with both tests.

For quiescence and stem cell analysis flow cytometry will be performed for cell cycle, CD44+CD24-CD45-Epcam+ and aldefluor. Samples will be divided into three replicates to address run variability. Total percent quiescent (G1/G0) epithelial cells will be the primary metric for correlative evaluation although quiescence within stem cell populations will be assessed and reported. All data are continuous variables.

Dichotomous analysis will be based on values > or <= to the median for the entire dataset for each variable. All biomarker analyses related to outcome will be performed according to REMARK guidelines incorporating time to metastases, extent of metastatic disease (multiple vs. effusion only), triple negative vs. not, extent of prior therapy, and KPS. Analysis will include correlation between percent quiescent cells and time to catheter removal in both arms and change in percent quiescent cells from baseline in both arms. Given there will be significant variation in the baseline G0/G1 measurement we will consider a 30% relative increase in G0/G1 from baseline significant.

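### Successful catheter removal ends pleural-fluid sampling, so week-6 and week-10 quiescence values come mainly from patients without the primary event, unequally by arm if VPA works

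*Combined protocol and SAP*

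**What the plan says.** Section 6.0, Translational Studies, makes the total percentage of quiescent (G1/G0) epithelial cells the primary correlative metric. It then states: "Analysis will include correlation between percent quiescent cells and time to catheter removal in both arms and change in percent quiescent cells from baseline", with the change examined in both arms. It names no visit for either analysis and gives no rule for patients who no longer have fluid.

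The source of the samples is in the fourth aim of Section 2.1: "Fluid will be collected and stored if applicable from visits at baseline, at week 2, 6, and 10". Section 3.4.9 has effusion collected at each clinic visit, and the text on evaluations beyond week 10 ends research sampling at week 10. The Study Parameters table marks the pleural fluid as optional.

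The primary event is removal because drainage is no longer needed. Section 7.1 allows that removal only after sustained low drainage and no sign of reaccumulation. The design effect in Section 6.0 is "detect an improvement in median time to catheter removal from 56 days in the control arm to 28 days (hazard ratio = 2.0"), and the same section gives 110 and 55 days as an alternative pair of medians.

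**The concern.** The primary event decides who can be measured later. A patient whose catheter comes out successfully has no catheter and, under Section 7.1, no reaccumulated fluid. The plan provides no other research sampling route.

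If quiescence speeds removal, patients with the largest rise leave the sampled group first, and they leave the VPA arm faster. Mean change at weeks 6 and 10 then describes the patients in whom the process has gone least far. A plain correlation of a week-6 or week-10 value with total time to removal is likewise limited to removal times beyond that visit.

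At stake is the reading of the trial's mechanism. Section 1.0 says that serial fluid samples are there to validate the translational hypothesis. Selection could understate a real effect on quiescence. It could also produce an apparent difference where there is none, if VPA shortens time to removal by another route.

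**Working it through.** **The plan's own figure.** The medians give a hazard ratio of (ln 2/28)/(ln 2/56) = 2.0. Section 6.0 says "A sample size of 76 patients (38 on each arm) will yield 80% power" "with a 2-sided significance level of 0.05". Schoenfeld's formula gives 4(1.960 + 0.842)²/(ln 2)² = 65.3, so 66 events. With 76 events, a fixed design has power 0.856. With the look at 36 removals and binding futility at two-sided 0.3217, power is 0.788, close to the stated 80%. The plan gives no figure for evaluable fluid samples.

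**Inputs.** 38 per arm; control/VPA medians of 56/28 or 110/55 days (Section 6.0); visits at days 14, 42 and 70. Section 1.1 gives a median survival of 7.4 months for breast cancer, about 225 days. Using it for this population is an assumption, as is the exponential shape.

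**Expected number alive with a catheter.** N(t) = 38 × exp(−(ln 2/m + ln 2/225) × t), where m is the median time to removal. The death hazard is ln 2/225 = 0.00308 per day. Examples at week 10 with 56/28 days:
- control: 38 × exp(−(0.01238 + 0.00308) × 70) = 38 × 0.339 = 12.9
- VPA: 38 × exp(−(0.02476 + 0.00308) × 70) = 38 × 0.142 = 5.4

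| Medians, control/VPA | Week 2 | Week 6 | Week 10 |
|---|---|---|---|
| 56/28 days | 31 vs 26 | 20 vs 12 | 13 vs 5 |
| 110/55 days | 33 vs 31 | 26 vs 20 | 20 vs 13 |

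Ignoring death, 0.5^(70/m) gives week-10 retention of 42% vs 18% at 56/28 days and 64% vs 41% at 110/55 days. Removal for other reasons, refusal and inadequate samples would lower the counts further.

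**Size of the selection (simulation; all parameters assumed).** VPA raises quiescence by 0.80 SD. The removal hazard is h0 × exp(0.866 × Q), where Q is the current level, so VPA's effect is exp(0.866 × 0.80) = 2.0 and acts through quiescence alone. h0 is set to give a control median of 56 days. Death has a median of 225 days. Total variance of Q is held at 1 and split between baseline and change. Results are for patients alive with a catheter:

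| Share of variance that is baseline | VPA mean change, weeks 2 / 6 / 10 | Arm difference at week 10 (true 0.80) |
|---|---|---|
| 0% | 0.51 / 0.18 / −0.04 | 0.51 |
| 50% | not shown | 0.66 |
| 80% | 0.74 / 0.68 / 0.63 | 0.74 |

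In the 0% row the control mean at week 10 is −0.55, and the arm differences at weeks 2 and 6 are 0.68 and 0.57. With 110/55 days and 0% baseline variance, the VPA mean at week 10 is 0.24 and the difference 0.59.

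**The opposite error.** A second simulation had no true arm difference in quiescence, all variation in the change, hazard ratios for removal of 1.35 to 2.7 per SD, and medians of 56/28 days. Patients still with a catheter at week 10 showed a spurious VPA-minus-control difference of −0.22 to −0.29 SD. At 110/55 days it was −0.12 to −0.22 SD.

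**The correlation.** In that simulation a rank correlation of −0.43 among all patients became about −0.36 among those with a catheter at week 10.

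**The case against.** The strongest reply is that part of the problematic analysis has to be supplied by the reader. Section 6.0 names no visit. A correlation of baseline quiescence with time to removal uses every patient with a baseline sample and is not conditioned on the event. A reader might infer that the planned correlation is a week-10 one, restricted to removal times over 70 days; the text does not say so. This stands for the correlation. It does not rescue change from baseline, which needs a later sample.

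The size is also open to challenge. A reader might infer that a true mechanism would vanish from the results. Only the single-arm VPA mean does that, and only if no between-patient variation is baseline variation. The plan itself expects the baseline measurement to vary considerably, and it looks at both arms. The arm difference remains at 0.51 to 0.74 of 0.80 SD. If every patient shifted by the same amount, change would carry no selection bias.

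A reader might also infer that most VPA patients have lost the catheter by week 6. That holds at 56/28 days (35% still have it, before deaths) but not at 110/55 days (59%). The 56-day figure is the lower confidence limit of the historical median of 110 days.

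Finally, Section 3.4.9 already collects effusion at each clinic visit, so a removal visit may yield a sample. Fluid drained after a later reaccumulation is also conceivable, although no such sampling is planned. So the later values come mainly, not exclusively, from patients without the event.

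**Conclusion.** The concern holds in a limited form. Sampling depends on not having had the primary event, and the plan has no method for this. If VPA works, the arms are depleted unequally: 13 vs 5 of 38 at week 10 under 56/28 days, 20 vs 13 under 110/55 days. Week-6 and week-10 changes, and any plain correlation of those values with total time to removal, are therefore subject to selection.

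The direction follows from the sampling rule if quiescence is linked to removal. The amount does not. Under 56/28 days the simulated loss at week 10 runs from slight (0.74 of 0.80 SD) to about a third (0.51 of 0.80 SD), depending on how much variation is baseline. The correlation is affected less. These figures rest on exponential removal times for the counts, the assumed survival, and an assumed link between quiescence and removal.

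The primary comparison, its sample size and the stopping rules are untouched. The change is worth making because it is cheap and this is the trial's test of its mechanism.

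**What to change.** In Section 6.0, Translational Studies:

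1. Replace the plain correlation with a Cox analysis of removal on quiescence. Use the baseline value plus a week-2 landmark (removal after week 2 among patients still with a catheter), or enter quiescence as a time-dependent covariate.
2. Make week 2, the least selected visit, the main between-arm comparison of change from baseline. Analyse weeks 2, 6 and 10 together in a repeated-measures model, not separately among patients still with a catheter. The model still assumes that absence of a sample can be explained by the values already observed.
3. Report the number sampled by arm and visit, and state that week-6 and week-10 means are not to be read as drug effect alone.
4. Confirm that collection at each clinic visit under Section 3.4.9 covers fluid drained at an unscheduled removal visit.

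The cost is SAP wording and, at most, keeping fluid that is drained anyway. Treatment, sample size and the primary analysis do not change. There are two drawbacks. Week 2 reflects little exposure after the dose increase, which Section 3.4 places after 10 tolerated days. Fluid may also be scant at removal, and the timing of such samples will vary between patients.

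### The 30% relative-increase cut-off for G0/G1 cannot be met from a baseline above 76.9%, and no between-arm test is named for this metric

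*Combined protocol and SAP*

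**What the plan says.** Section 6.0, Translational Studies, sets out the flow cytometry analysis. "Total percent quiescent (G1/G0) epithelial cells will be the primary metric for correlative evaluation", and "All data are continuous variables". Each sample is run in triplicate: "Samples will be divided into three replicates to address run variability". Two analyses are listed: the correlation of percent quiescent cells with time to catheter removal in both arms, and "change in percent quiescent cells from baseline in both arms". A median split is also described for dichotomous analyses.

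The paragraph closes with the cut-off and its reason: "Given there will be significant variation in the baseline G0/G1 measurement", "we will consider a 30% relative increase in G0/G1 from baseline significant".

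The text does not derive the 30% from assay error or any stated variance. It does not say whether the cut-off applies to a patient or to an arm mean, or which follow-up visit it uses. Section 2.1 has fluid taken at baseline and at weeks 2, 6 and 10. No between-arm test, significance level or power is given for G0/G1. Under Secondary Outcomes, by contrast, the same section names an arm comparison for drainage, tumor burden and quality of life.

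**The concern.** Section 1.3 proposes that valproic acid works by making tumor cells quiescent, and Section 1.0 gives the serial fluid samples the task of validating the translational hypothesis. G0/G1 is the most direct reading of that mechanism, so how a change is judged matters for what the trial can say about biology.

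Two separate problems arise.

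- **Ceiling.** A fixed relative increase on a scale that ends at 100% becomes harder to reach as baseline rises, and then impossible. A real effect in patients with high baseline quiescence could fail to register. Baseline variation is the plan's reason for the cut-off, yet it is also what makes the hurdle uneven between patients.
- **No named contrast.** A change from baseline within one arm mixes drug effect with everything else that happens over the same weeks. Section 5.1.6 allows concurrent hormonal or systemic chemotherapy. Only the comparison with placebo separates these, and the plan does not specify one for this metric.

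The first problem risks a missed effect, the second a spurious one.

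**Working it through.** The plan gives no operating characteristic for the cut-off, so there is no figure to reproduce.

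**1. The ceiling (exact).** Meeting the cut-off requires 1.30 × baseline ≤ 100, so baseline ≤ 100/1.30 = 76.92%.

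| Baseline | Value needed | Rise in points |
|---|---|---|
| 30% | 39% | 9 |
| 50% | 65% | 15 |
| 60% | 78% | 18 |
| 70% | 91% | 21 |
| 75% | 97.5% | 22.5 |
| 77% | 100.1% | impossible |

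The largest possible relative increase is 100/baseline − 1: 25.0% from 80%, 17.6% from 85% and 11.1% from 90%. If the cut-off were applied to the ratio of arm means, the same limit would hold for the arm's mean baseline.

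**2. How many samples lie above the ceiling (assumed inputs).** Taking baseline as beta-distributed with an assumed mean and SD:

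| Mean baseline | SD 10 points | SD 15 points |
|---|---|---|
| 50% | 0.2% | 3.5% |
| 60% | 3.9% | 13.6% |
| 70% | 26.2% | 36.6% |
| 80% | 66.0% | 64.8% |
| 85% | 80.6% | 76.2% |

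**3. What a given effect looks like under the cut-off (assumed inputs).** Suppose the odds of quiescence double. Without noise, baseline b moves to 2b/(1 + b), a ratio of 2/(1 + b). That reaches 1.30 only if b ≤ 2/1.30 − 1 = 53.8%. Simulation with baseline SD 10 points and a logit SD of change of 0.25 to 0.5 gives the chance that a patient meets the cut-off as 52–55% at mean baseline 50%, 10–15% at 70% and 3–4% at 80%. With no drug effect, 1–11% still meet it at mean baseline 50%, and under 1% at 80%.

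**4. What a between-arm comparison could detect.** With 38 evaluable per arm, two-sided 0.05 and 80% power, the detectable difference is (1.960 + 0.842) × √(2/38) = 0.64 SD of the change. The documents give no SD to convert this to points. On the assumptions of step 3, doubled odds is ln 2 = 0.693 on the logit scale, or 0.693/0.5 = 1.4 to 0.693/0.25 = 2.8 SD. This is an arm-level quantity and is not directly comparable with the patient-level chances in step 3.

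**5. Which visit.** Fluid is obtainable mainly while the catheter is in. With the design medians in Section 6.0 (28 days active, 56 control), exponential times and no deaths, the share with a catheter at day t is 2^(−t/median).

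- Week 2 (t = 14): 2^(−0.5) = 71% active, 2^(−0.25) = 84% control.
- Week 6 (t = 42): 2^(−1.5) = 35% active, 2^(−0.75) = 59% control.

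At week 2 that is about 38 × 0.71 = 27 and 38 × 0.84 = 32 patients, and the detectable difference becomes 2.802 × √(1/27 + 1/32) = 0.73 SD. With the alternative medians in the same section (55 and 110 days), the shares are 84% and 92% at week 2, and 59% and 77% at week 6.

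**The case against.** The strongest reply is that the cut-off decides little. The data are kept continuous, and neither listed analysis depends on the 30% line; a true change short of 30% would still appear in the continuous change from baseline. The metric enters no stopping rule, sample size or primary analysis, and quiescence is not itself a listed objective in Sections 2.2 and 2.3. The word *significant* may mean no more than noteworthy, since the same sentence also uses it loosely of baseline variation. Scaling to each patient's own baseline is a recognizable response to varied baselines. All of this stands and keeps the point minor. It does not remove the ceiling or supply the missing contrast.

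A reader might go further in four ways that the documents do not support.

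- **That placebo is ignored.** Change is to be examined in both arms of a randomized, blinded trial. The comparator is there; the test is not named.
- **That both defects hide true effects.** Only the ceiling does. The unnamed contrast mainly lets other influences pass as drug effect.
- **That highly quiescent patients are classed as failures.** No responder or failure status is defined for G0/G1, and the patient-level reading is itself an assumption.
- **That low-baseline patients will pass through regression to the mean.** The documents give no error figure from which to judge this. The no-effect simulation gives 1–11% at mean baseline 50%, but it does not build in regression to the mean. Triplicate runs reduce part of the noise.

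A fair objection to the remedy is that fluid is lost as catheters come out, unequally by arm if the drug works, and that the study schedule lists pleural fluid as optional. This is why the visit must be named.

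**Conclusion.** The point holds as a minor one. The 76.9% limit is exact and needs no outside figure, and the unequal hurdle below it follows from the same arithmetic. The cut-off can therefore miss a true effect at high baselines. How often cannot be stated: the 0.2% to 81% range rests wholly on assumed baseline means of 50–85% and SDs of 10–15 points, so the documents cannot show whether the loss is trivial or serious. Separately, the absence of a named between-arm test leaves a false-positive risk that a randomized comparison would remove. The consequence is confined to interpretation of the mechanism; time to catheter removal and the 76-patient sample size do not depend on it.

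**What to change.** In Section 6.0, Translational Studies, base the G0/G1 inference on a between-arm ANCOVA: follow-up G0/G1 (averaged over replicates, for example on the logit scale) on baseline and arm, with the estimated difference and its confidence interval.

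Name one visit, preferably week 2, when under the design medians most catheters are still in place in both arms. Section 2.1 already uses baseline and week 2 for histone acetylation and cytokines. Report weeks 6 and 10 descriptively, with the number sampled per arm. Report the 30% cut-off, if kept, only as a descriptive proportion in both arms, stating that it is applied per patient and how many baselines exceed 76.9%.

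The cost is wording; no new samples or visits are needed. There are two trade-offs. The comparison covers only patients with evaluable fluid at that visit, so the number missing and the reason should be given by arm. Week 2 also falls close to the planned dose step (after 10 tolerated days, Section 3.4), so the result mainly describes early exposure and should be reported as such.
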